7.3. Lost to follow-up

A participant will be considered lost to follow-up if the participant repeatedly fails to complete follow-up contacts (or scheduled visits) and is unable to be contacted by the study site.

A participant will be considered ‘provisional lost to follow-up’ if the participant is considered lost to follow-up but has not reached the end of the study follow-up period. Unless there is a compelling reason, participants with a provisional lost to follow-up status should not receive further study-related contact from the study sites. A provisional lost to follow-up participant who subsequently contacts the site and wants to resume follow-up may resume study activities, provided that the participant has not reached the end of the study follow-up period.

The following actions must be taken if a participant fails to complete a follow-up contact (or fails to return to the clinic for a required study visit):

1. The site must attempt to contact the participant and reschedule the missed visit or follow-up contact as soon as possible, counsel the participant on the importance of maintaining the assigned visit schedule or follow-up contact and ascertain whether the participant wishes to and/or should continue in the study.
2. Before a participant is deemed lost to follow-up, the investigator or designee must make every effort to regain contact with the participant (where possible, [3] telephone calls, and if necessary, a certified letter to the participant’s last known mailing address or local equivalent methods). These contact attempts should be documented in the participant’s medical record.
3. The site will then mark the participant as provisional lost to follow-up. This designation can be removed if the participant recontacts the site to resume study follow-up before the end of their study follow-up period.

4. Should the participant continue to be unreachable, the participant will be considered to have withdrawn from the study.
5. Final lost to follow-up status should be determined at the end of the study when a **participant** has reached the end of the study follow-up period (e.g., 2 years post-vaccine/control + 2 months) without returning for or responding to one or more of his/her final study visits or study contacts. The date of last participant contact will be considered to be the date of study withdrawal for lost to follow-up.

8. STUDY ASSESSMENTS AND PROCEDURES

6. Study procedures and their timing are summarized in the Schedule of Activities (SoA) (Section 1.3). Protocol waivers or exemptions are not allowed.
7. Adherence to the study design requirements, including those specified in the SoA (Section 1.3), is essential and required for study conduct.
8. All screening evaluations must be completed and reviewed to confirm that potential participants meet all eligibility criteria.
9. In the event of a significant study-continuity issue (e.g., caused by a pandemic), alternate strategies for participant visits and monitoring may be implemented by the sponsor or the investigator, as per local health authority/ethics requirements.

8.1. Administrative and general/baseline procedures

8.1.1. Collection of demographic data and lifestyle characteristics

Record demographic data such as date of birth, **sex (for infant participants)**, race, and ethnicity in the participant's eCRF. Record lifestyle characteristics data such as smoking and substance use in the participant's eCRF will be collected towards the end of pregnancy.

Collection of sex, race and ethnicity data is necessary to assess and monitor the diversity of the participants, and to determine if the participants are truly representative of the impacted population.

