1.3. Schedule of activities (SoA)

Table 1 Study activities for retrospective cohort

Type of contact	Visit 1/Contact 1	Notes
Timepoint	Day 1 ^c	
Participant Contact ^a	•	
Informed consent	•	Maternal and infant informed consent
Inclusion and exclusion criteria	•	
Demography and lifestyle characteristics	•	Mothers: Demography at enrollment, and lifestyle during or at the end of each pregnancy Infants: Demography at birth, and lifestyle at Day 42 post-delivery
Medical and vaccination history	•	Collect information prior to start of study pregnancies (for each pregnancy)
Contact information for all HCPs seen by mother or infant from start of current study pregnancies through day 42 post-delivery	○	
Safety assessments during current study pregnancies (from medical record review)		
Record concomitant medications/vaccinations	•	One month prior to conception to Day 42 post-delivery
Record medically attended AEs ^b until Day 42 post-delivery	•	Mothers: conception to Day 42 post-delivery Infants: birth to Day 42 post-delivery
Record pregnancy outcomes, pregnancy AESIs until Day 42 post-delivery and infant AESIs until Day 42 post-delivery	•	
Infant SAEs from birth until Day 42 post-delivery	•	
Infant MAEs from birth until Day 42 post-delivery	•	
SAEs during pregnancy until Day 42 post-delivery	•	
Record SAEs related to study participation or related to a GSK product ^d	•	
Final Activities		
Study conclusion	•	

• Is used to indicate a study procedure that requires documentation in the individual eCRF.

○ Is used to indicate a study procedure that does not require documentation in the individual eCRF.

^a Contact may be via telephone, SMS, email, video-telephone/telemedicine or other means, depending on local best practice. If the study site is the participant's primary healthcare facility, contact with study personnel may also be made in the context of a visit for routine or event-driven care

^b events reported in the context of routine follow-up or unrelated to the event causing an event-driven visit will not be counted as 'medically attended' (e.g., a minor URI noted in the context of a routine prenatal visit would not be a 'medically attended event')

^c All information needed for retrospective cohort participants can likely be collected on a single day, but it is possible that study personnel may need to re-contact participants to complete/clarify data collection.

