^d **Any SAEs assessed as related to study participation (e.g., protocol-mandated procedures) or related to a GSK product will be recorded from the time a participant consents to participate in the study.**

CONFIDENTIAL

219510 (RSV MAT-015)
Protocol Amendment 2 Final

Table 2 Schedule of Activities for prospective cohort – Adult/Adolescent participant

Type of contact	Visit 1/Contact 1 ^a	Follow-up contact ^a	Unscheduled contact ^a	Initial Pregnancy Contact ^{a, b}	Pregnancy contacts	Delivery ^b	Day 42 Contact ^b	Notes
Timepoints	Day 1	Bi-annual, to 2 years+2 months post vaccine/control			Monthly until delivery**		Day 42 post-delivery	
Informed consent/Informed Assent	•							
Inclusion and exclusion criteria	•							
Demography and lifestyle characteristics	•					•		Demography at enrollment, and lifestyle during or at the end of each pregnancy
Medical and vaccination history prior to pregnancy	•			•				Collect information prior to start of study pregnancies
Spontaneous pregnancy reporting by participants	•	•	•	•	•	•	•	
Contact information for all HCPs seen from start of current study pregnancies through day 42 post-delivery	○	○	○	○	○	○	○	
Safety assessments during current study pregnancies (from medical record review)								
Record medications/vaccinations	•			•	•	•	•	One month prior to conception to Day 42 post-delivery
Record medically attended AEs until Day 42 post-delivery	•			•	•	•	•	Conception to Day 42 post-delivery
Record pregnancy outcomes, pregnancy related AESIs until Day 42 post-delivery	•		•	•	•	•	•	
SAEs during pregnancy until Day 42 post-delivery	•			•	•	•	•	

CONFIDENTIAL

219510 (RSV MAT-015)
Protocol Amendment 2 Final

Type of contact	Visit 1/Contact 1 ^a	Follow-up contact ^a	Unscheduled contact ^a	Initial Pregnancy Contact ^{a, b}	Pregnancy contacts	Delivery ^b	Day 42 Contact ^b	Notes
Timepoints	Day 1	Bi-annual, to 2 years+2 months post vaccine/control			Monthly until delivery**		Day 42 post-delivery	
Record SAEs related to study participation or related to a GSK product ^d	•	•	•	•	•	•	•	
MAEs, SAEs and AEs (AESIs) leading to study withdrawal	•	•	•	•	•	•	•	
Final Activities								
Study conclusion		• ^c					• ^c	

• Is used to indicate a study procedure that requires documentation in the individual eCRF.

○ Is used to indicate a study procedure that does not require documentation in the individual eCRF.

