^a Any study contact may be via telephone, SMS, email, video-telephone/telemedicine or other means, depending on local best practice. If the study site is the participant's primary healthcare facility, contact with study personnel may also be made in the context of a visit for routine or event-driven care.

^b May be combined with another contact where pregnancy is first reported [e.g., combined with Visit 1/Contact 1 (for past/ongoing pregnancies at enrollment), follow-up contact, unscheduled contact.]

^c For participants who are not pregnant at 2 years post vaccine/control, the study conclusion will be completion of the last bi-annual contact, at least 2 months after 2 years post-vaccine/control. If the participant is pregnant at 2 years post vaccine/control **or at study enrollment**, study conclusion will be completion of Day 42 post-delivery. **WONCBP at study enrollment, or recipient of bilateral tube ligation prior to study enrollment will be excluded from the study if she has not conceived a pregnancy post-vaccine/control and does not plan to use any additional measures to attempt to conceive a pregnancy (e.g., sterilization reversal or in vitro fertilization (IVF)).**

^d Any SAEs assessed as related to study participation (e.g., protocol-mandated procedures) or related to a GSK product will be recorded from the time a participant consents to participate in the study.

Table 3 Schedule of Activities for prospective cohort – Infant participant

Type of contact ^a	Delivery ^b	Day 42 Contact ^b	Notes
Timepoints	Day 1	Day 42	
Informed consent	•		Infant informed consent is anticipated at delivery, but may be done at any time up to the delivery contact if allowed at the site (or at Visit 1/Contact 1 for an infant born from a past pregnancy)
Inclusion and exclusion criteria	•		
Demography and lifestyle characteristics	•	•	Demography at birth, and lifestyle at Day 42 post-delivery
Contact information for all HCPs seen by infant from birth through Day 42	○	○	
Safety assessments (from medical record review)			
Record medications/vaccinations	•	•	
Record medically attended AEs until Day 42	•	•	
Infant AESIs from birth until Day 42	•	•	
Infant SAEs from birth until Day 42	•	•	
Record SAEs related to study participation or related to a GSK product ^c	•	•	
MAEs, SAEs and AEs (AESIs) leading to study withdrawal	•	•	
Final Activities			
Study conclusion		•	

• Is used to indicate a study procedure that requires documentation in the individual eCRF.

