5.1. Inclusion criteria

5.1.1. Retrospective cohort

Adult/Adolescent Participant:

- Adult/Adolescent study participant, from *any of the prior RSV MAT* studies who have either received RSV MAT vaccine or control (placebo, Tdap or influenza vaccine).
- Study participant:
 - Who has reached 2 years+2 months post vaccine/control prior to/at enrollment or
 - who has not reached 2 years+2 months post vaccine/control prior to/at enrollment but is a Woman of Nonchildbearing Potential (WONCBP) as defined in Section 10.3.1.2 at study enrollment, or recipient of bilateral tubal ligation prior to study enrollment.
- Study participant with any pregnancy conceived post-vaccination/control, that has reached Day 42 post-delivery prior to/at enrollment.
- Provide signed and dated informed consent form.
- Be willing to comply with all study requirements and be available for the duration of the study.

Infant Participant:

- Participant live born as the result of a pregnancy followed in an adult/adolescent participant in this study.
- Signed and dated informed consent form obtained from the participant's parent(s)/LAR(s) prior to performance of any study-specific procedure.

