Infant participants	Number and percentage of infant participant reporting infant AESIs from any study pregnancy conceived within 2 years post-vaccination in participants enrolled in prior RSV MAT studies up to Day 42 post-delivery.	The Number and percentage of infant participant reporting infant AESIs from any pregnancy conceived within 2 years post-vaccination in participants enrolled in prior RSV MAT studies up to Day 42 post-delivery , will be tabulated with its exact 95% CI by study arms on subject level. By participant listings of infant AESIs will be prepared.

9.3.3.2. **Selected pregnancy outcomes and AESIs by selected risk factors**

The number and percentage of selected pregnancy outcomes, pregnancy related AESIs and infant AESIs by study arms, stratified by selected risk factors, will be tabulated with exact 95% CIs for both first and any study pregnancy **conceived within 2 years post-vaccination in participants enrolled in prior RSV MAT studies up to Day 42 post-delivery.** Their relative risk estimates with 95% CIs and observed p-values will be reported for all comparisons accordingly.

Regarding preterm birth outcome, the comparisons will be conducted by study arms and by the combination of study arms and preterm birth history (Yes/No) in prior MAT study. The risk factors to be explored may include maternal smoking/household smoke exposure, maternal substance abuse, infections during pregnancy, COVID infection during pregnancy, prior preterm delivery, multiple gestation pregnancy, and short inter-pregnancy interval (less than 18 months between pregnancies), pregnancy complications such as preeclampsia and fetal distress.

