6.1.2. Demographic and Baseline Characteristics

These analyses will be performed on the Enrolled set and on the Full Analysis Set.

For all maternal participants, demographic characteristics (e.g., age at previous study vaccine administration <18, 18-24, 25-34 and ≥ 35 years; overall), age at 1st and 2nd pregnancy, gestational age at birth (≥ 37 weeks or < 37 weeks), other baseline and lifestyle characteristics will be summarized by arm using descriptive statistics. The interval in days between previous RSV MAT study delivery and current study pregnancy will be calculated and summarized by arm using descriptive statistics.

For infants, demographic characteristics (e.g., gestational age at time of delivery (≥ 37 weeks; < 37 weeks), sex, weight, length, head circumference, race and ethnicity), and lifestyle characteristics (e.g., living environment, household composition, breastfeeding, passive smoking and extent of contact with children less than 6 YOA) will be summarized by arm using descriptive statistics.

Past medical conditions and current medical conditions as of screening will be summarized respectively.

Demographics and baseline characteristics as well as the lifestyle characteristics may be reported by CCI [REDACTED]

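### For pregnancies conceived after enrolment, smoking and substance use have no scheduled record before the outcome is known, and the protocol's three statements of timing do not agree

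*Protocol*

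**What the plan says.** The timing of maternal lifestyle data is given in three places.

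- Protocol Section 8.1.1: "smoking and substance use in the participant's eCRF will be collected towards the end of pregnancy".
- The note in Protocol Table 2 (prospective cohort, mothers): "Demography at enrollment, and lifestyle during or at the end of each pregnancy". Table 1 (retrospective cohort) has the same wording.
- The grid of Table 2: the lifestyle row has a mark at Visit 1 and, counting columns, at Delivery. It has none at the Initial Pregnancy Contact or the monthly pregnancy contacts. Medical history, medications and medically attended events are all marked at the Initial Pregnancy Contact.

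Table 4 plans the Delivery contact three days after delivery and allows it up to Day 42. Protocol Section 8 makes adherence to the schedule mandatory.

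The variables are used in a secondary analysis. Protocol Section 9.3.3.2 names among the candidate risk factors "maternal smoking/household smoke exposure, maternal substance abuse, infections during pregnancy", and SAP 4.3.2.2 carries them forward, with the final list to be fixed before the final analysis. Results are tabulated by study arm within risk-factor strata, with relative risks and p-values. SAP 4.6.1 adds an optional logistic regression. SAP 4.1.1 leaves missing values unimputed and out of the analysis.

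In the retrospective cohort, Section 5.1.1 requires a pregnancy "that has reached Day 42 post-delivery prior to/at enrollment", and a footnote to Table 1 adds that "All information needed for retrospective cohort participants can likely be collected on a single day". There the outcome is always known when the question is asked, and no schedule could change that.

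**The concern.** A prospective cohort should be able to record exposure before the outcome. Here women who conceive after enrolment are contacted monthly through pregnancy, but the schedule opens the lifestyle item only after delivery. A mother who has just had a preterm birth may describe her smoking or substance use differently from a mother who has not. She may search her memory harder and report more, or feel blamed and report less.

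The second risk is a gap related to outcome. Spontaneous abortion and termination are counted outcomes, but a prospective pregnancy ending that way has no named contact at which lifestyle is taken. If sites follow the grid literally, the item may stay blank for those pregnancies, and they would then drop out of the strata.

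At stake are the event rates within the smoking and substance-use strata, and any regression that uses these factors. The limitations in Protocol Section 4.5 mention recall bias only for the incidence of AESIs in the retrospective data, not for exposures.

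**Working it through.** The plan gives no figure on this point, so the check compares the texts and then illustrates the size with assumed values.

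**Step 1. When is the exposure first asked?**

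| Pregnancy | Scheduled lifestyle record | Outcome known? |
|---|---|---|
| Completed before enrolment | Visit 1 | Yes, always |
| Ongoing at enrolment | Visit 1, then Delivery | Not known at Visit 1 if still undelivered |
| Conceived after enrolment | Delivery (3 days after birth, up to Day 42) | Yes |
| Conceived after enrolment, lost early | No contact named | Not defined |

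In the third row, the Visit 1 record predates the pregnancy. Section 8.1.1 points to late pregnancy, the Table 2 note to any time in pregnancy or its end, and the grid to after the birth. Neither text names a contact during a newly conceived pregnancy.

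**Step 2. Effect on the rates within strata.** Assumptions, none from the documents: 600 pregnancies, 7% preterm (42 cases, 558 non-cases), 15% true smokers in both, no true effect, no false reports of smoking.

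Reported smokers among cases: a = 42 × 0.15 × s1. Among non-cases: b = 558 × 0.15 × s0. Here s1 and s0 are the shares of true smokers who report it. Rate in reported smokers = a/(a+b). Rate in reported non-smokers = (42−a)/(600−a−b).

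| s1 | s0 | a | b | Rate, smokers | Rate, non-smokers | Ratio |
|---|---|---|---|---|---|---|
| 0.95 | 0.85 | 5.985 | 71.145 | 7.8% | 6.9% | 1.13 |
| 0.95 | 0.75 | 5.985 | 62.775 | 8.7% | 6.8% | 1.28 |
| 0.95 | 0.65 | 5.985 | 54.405 | 9.9% | 6.7% | 1.48 |
| 0.75 | 0.95 | 4.725 | 79.515 | 5.6% | 7.2% | 0.78 |

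The true values are 7.0%, 7.0% and 1.00. The last row shows that the bias can run downwards.

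**Step 3. Effect on the arm contrast within strata.** Split 300/300 by arm, with the same reporting in both arms.

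- 7% preterm in both arms: the arm relative risk is 1.00 in both strata for every s0.
- 8% against 6% (true relative risk 8/6 = 1.33), s1 = 0.95, s0 = 0.65. Reported smokers in the first arm: 24 × 0.15 × 0.95 = 3.42 cases and 276 × 0.15 × 0.65 = 26.91 non-cases, rate 3.42/30.33 = 11.28%. In the second arm: 18 × 0.15 × 0.95 = 2.565 and 282 × 0.15 × 0.65 = 27.495, rate 2.565/30.06 = 8.53%. Ratio 1.32. With s0 = 0.85 or 0.75 it is 1.33. Reported non-smokers give 1.33 each time.
- Recall that differs by arm: 7% in both arms, s0 = 0.75 in both, s1 = 0.95 in one arm and 0.75 in the other. Rates among reported smokers are 2.9925/(2.9925+31.3875) = 8.7% and 2.3625/(2.3625+31.3875) = 7.0%, a ratio of 1.24 where the truth is 1.00.

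**Step 4. Possible gaps.** The plan expects about 650 participants with a pregnancy. If an assumed 5% to 20% ended early without a lifestyle record, 650 × 0.05 = 32.5 to 650 × 0.20 = 130 would leave the strata. This is a ceiling, because it treats all 650 as conceived after enrolment and every loss as unrecorded.

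**The case against.** The strongest reply is that the planned comparison is study arm within strata, not smokers against non-smokers. This stands: ratios such as 1.13 to 1.48 do not describe bias in the planned arm contrast, which Step 3 shows is nearly unmoved when recall is the same in both arms. They bear on the rates within strata and on the optional logistic model. Differential recall by arm remains possible, since Protocol Section 4.5 says participants know which product they received, but nothing in the documents shows that it occurs.

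Three stronger readings are tempting and go too far.

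- A reader might infer that exposure is never recorded for a pregnancy lost before delivery. The notes in Tables 1 and 2 cover the end of each pregnancy, and losses completed before enrolment can be asked about at Visit 1. A Table 2 footnote also lets contacts be combined where a pregnancy is first reported, though that does not help one already under monthly follow-up. The supportable point is that the contact is not named.
- A reader might infer that exposure is usually recorded after the outcome. The documents do not give the split between completed, ongoing and later pregnancies.
- A reader might infer that an infant who dies has no smoke-exposure record, because infant data are timed as "Demography at birth, and lifestyle at Day 42 post-delivery" and SAP 6.1.2 lists "breastfeeding, passive smoking and extent of contact with children". That is a descriptive infant characteristic. Nothing says the household-smoke risk factor is drawn from the infant form, or that the Day 42 contact with the parent lapses after a death.

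Timing is a further fair objection. Vaccination stopped on 28 February 2022, so eligible conceptions within two years ended by about 28 February 2024. Assuming 266 days to birth, the last births fall about 20 November 2024 and Day 42 about 1 January 2025, before the current SAP of 17 February 2025. On these dates the schedule change may come too late for most or all of the pregnancies concerned. The analysis and reporting parts of the fix do not.

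Finally, collection at the end of pregnancy captures changes in behaviour. That is a reason to keep the late record, not to omit an early one.

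**Conclusion.** The point holds in a limited form. For prospective pregnancies conceived after enrolment, Table 2 provides no lifestyle record during pregnancy before the outcome, names no contact for an early loss, and disagrees with its own note and with Section 8.1.1.

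The likely effect is on incidences within the smoking and substance-use strata and on any model using those factors. Under the assumed reporting differences, a true 7.0% among smokers would appear as anything from 5.6% to 9.9%. The direction cannot be predicted. The arm contrast within strata is little affected unless recall differs by arm, and the primary incidence by arm does not use these variables.

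The conclusion assumes that the Table 2 marks are read in the correct columns. It also assumes that lifestyle data come from interview. The documents do not state the source, but the row sits outside the block taken from medical records. The factors are candidates, and the analysis is descriptive. This is a worthwhile, inexpensive improvement, not a threat to the main results.

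**What to change.** **Protocol.** In Table 2, add the lifestyle item (maternal smoking, household smoke exposure, substance use) at the Initial Pregnancy Contact, and update it when the pregnancy ends by any outcome, naming the contact for an early loss. Reword Section 8.1.1 and the Table 2 note to match.

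**SAP 4.3.2.2.** Define exposure from all records within the pregnancy. Add a sensitivity analysis restricted to values recorded before the outcome. Report missing lifestyle data by pregnancy outcome and by arm.

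**Pregnancies already completed.** These cannot be improved. Report the date and source of the exposure data, and name outcome-dependent reporting as a limitation for these strata.

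**Cost.** A few minutes at a contact that already takes history and medications, one existing eCRF page opened earlier, and short edits to Table 2, Section 8.1.1 and SAP 4.3.2.2. If no pregnancy is still to be followed, only the SAP and reporting changes remain.
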